6.3 Assessing and Recording Adverse Events

An adverse event is defined as any untoward medical occurrence in a patient or clinical investigation subject administered a pharmaceutical product and which does not necessarily have to have a causal relationship with this treatment. An adverse event can therefore be any unfavorable and unintended sign (including a clinically significant abnormal laboratory finding, for example), symptom, or disease temporally associated with the use of a medicinal product or protocol-specified procedure, whether or not considered related to the medicinal product or protocol-specified procedure. Any worsening (i.e., any clinically significant adverse change in frequency and/or intensity) of a preexisting condition that is temporally associated with the use of the Merck's product, is also an adverse event.

Merck product includes any pharmaceutical product, biological product, device, diagnostic agent or protocol-specified procedure, whether investigational (including placebo or active comparator medication) or marketed, manufactured by, licensed by, provided by or distributed by Merck for human use.

Adverse events may occur during the course of the use of Merck product in clinical trials or within the follow-up period specified by the protocol, or prescribed in clinical practice, from overdose (whether accidental or intentional), from abuse and from withdrawal.

Adverse events may also occur in screened subjects during any pre-allocation baseline period as a result of a protocol-specified intervention, including washout or discontinuation of usual therapy, diet, placebo treatment or a procedure.

Progression of the cancer under study is not considered an adverse event unless it is considered to be drug related by the investigator.

All adverse events will be recorded from the time the consent form is signed through 30 days following cessation of treatment and at each examination. Adverse events will be recorded on an Adverse Event log and entered in OnCore within 72 hours of the site becoming aware of the event.. The reporting timeframe for adverse events meeting any serious criteria is described in section 6.3.3.1.

6.3.1 Definition of an Overdose for This Protocol and Reporting of Overdose to the Sponsor and to Merck

For purposes of this trial, an overdose of pembrolizumab will be defined as any dose of 1,000 mg or greater (≥ 5 times the indicated dose). No specific information is available on the treatment of overdose of pembrolizumab. Appropriate supportive treatment should be provided if clinically indicated. In the event of overdose, the subject should be observed closely for signs of toxicity. Appropriate supportive treatment should be provided if clinically indicated.

If an adverse event(s) is associated with (“results from”) the overdose of a Merck product, the adverse event(s) is reported as a serious adverse event, even if no other seriousness criteria are met.

If a dose of Merck’s product meeting the protocol definition of overdose is taken without any associated clinical symptoms or abnormal laboratory results, the overdose is reported as a non-serious Event of Clinical Interest (ECI), using the terminology “accidental or intentional overdose without adverse effect.”

All reports of overdose with and without an adverse event must be reported within 24 hours to the project manager. The project manager will report all overdoses within 2 working days to Merck Global Safety. (Attn: Worldwide Product Safety; [contact]). Sites are responsible for reporting to their IRB per local policy.

6.3.2 Reporting of Pregnancy and Lactation to the Sponsor and to Merck

Although pregnancy and lactation are not considered adverse events, it is the responsibility of investigators or their designees to report any pregnancy or lactation in a subject (spontaneously reported to them), including the pregnancy of a male subject's female partner that occurs during the trial or within 120 days of completing the trial completing the trial, or 30 days following cessation of treatment if the subject initiates new anticancer therapy, whichever is earlier. All subjects and female partners of male subjects who become pregnant must be followed to the completion/termination of the pregnancy. Pregnancy outcomes of spontaneous abortion, missed abortion, benign hydatidiform mole, blighted ovum, fetal death, intrauterine death, miscarriage and stillbirth must be reported as serious events (Important Medical Events). If the pregnancy continues to term, the outcome (health of infant) must also be reported.

Such events must be reported within 24 hours to the project manager. The project manager will report these events within 2 working days to Merck Global Safety. (Attn: Worldwide Product Safety; [contact]). Sites are responsible for reporting to their IRB per local policy.

6.3.3 Immediate Reporting of Adverse Events to the Sponsor and to Merck

6.3.3.1 Serious Adverse Events

A serious adverse event is any adverse event occurring at any dose or during any use of Merck’s product that:

- Results in death;
- Is life threatening;
- Results in persistent or significant disability/incapacity;
- Results in or prolongs an existing inpatient hospitalization;
- Is a congenital anomaly/birth defect;
- Is a new cancer (that is not a condition of the study);
- Is associated with an overdose;

Product: Pembrolizumab

43

Protocol/Amendment No.: Version 6.1 (10.10.2018)

- Is an other important medical event

Refer to Table 6 for additional details regarding each of the above criteria.

Any serious adverse event, or follow up to a serious adverse event, including death due to any cause other than progression of the cancer under study that occurs to any subject from the time the consent is signed through 90 days following cessation of treatment, or the initiation of new anti-cancer therapy, whichever is earlier, whether or not related to Merck product, and any unexpected Serious Adverse Event that occurs more than 90 days after drug administration but is possibly, probably or definitely attributed to drug administration, must be reported within 24 hours to the Yale project manager and protocol PI. The Yale project manager will report within 2 working days to Merck Global Safety. Sites are responsible for reporting to their IRB per local policy.

Non-serious Events of Clinical Interest will be forwarded to Merck Global Safety and will be handled in the same manner as SAEs.

Additionally, any serious adverse event, considered by an investigator who is a qualified physician to be related to Merck product that is brought to the attention of the investigator at any time outside of the time period specified in the previous paragraph also must be reported immediately to the Yale project manager who will then report to Merck. All SAEs should be entered into OnCore within 24 hours of the site becoming aware of the event.

SAE reports and any other relevant safety information are to be forwarded to the Merck Global Safety [contact]

A copy of all 15 Day Reports and Annual Progress Reports submitted as required by FDA, European Union (EU), Pharmaceutical and Medical Devices agency (PMDA) or other local regulators. Investigators will cross reference this submission according to local regulations to the Merck Investigational Compound Number (IND, CSA, etc.) at the time of submission. Additionally investigators will submit a copy of these reports to Merck & Co., Inc. (Attn: Worldwide Product Safety; [contact]) at the time of submission to FDA.

All subjects with serious adverse events must be followed up for outcome.

6.3.3.2 Events of Clinical Interest

Selected non-serious and serious adverse events are also known as Events of Clinical Interest (ECI) and must be recorded as such on the Adverse Event case report forms/worksheets and reported within 24 hours to the project manager and protocol PI. The project manager will report within 2 working days to Merck Global Safety. (Attn: Worldwide Product Safety; [contact]).

Events of clinical interest for this trial include:

1. an overdose of Merck product, as defined in Section 6.3.1 - Definition of an Overdose for This Protocol and Reporting of Overdose to the Sponsor, that is not associated with clinical symptoms or abnormal laboratory results.
2. an elevated AST or ALT lab value that is greater than or equal to 3X the upper limit of normal and an elevated total bilirubin lab value that is greater than or equal to 2X the upper limit of normal and, at the same time, an alkaline phosphatase lab value that is less than 2X the upper limit of normal, as determined by way of protocol-specified laboratory testing or unscheduled laboratory testing.*

***Note:** These criteria are based upon available regulatory guidance documents. The purpose of the criteria is to specify a threshold of abnormal hepatic tests that may require an additional evaluation for an underlying etiology. The trial site guidance for assessment and follow up of these criteria can be found in the Investigator Trial File Binder (or equivalent).

ECIs (both non-serious and serious adverse events) identified above from the date of first dose through 90 days following cessation of treatment, or 30 days after the initiation of a new anticancer therapy, whichever is earlier, need to be reported within 24 hours to the Sponsor and within 2 working days to Merck Global Safety. (Attn: Worldwide Product Safety; [contact]), regardless of attribution to study treatment, consistent with standard SAE reporting guidelines.

Subjects should be assessed for possible ECIs prior to each dose. Lab results should be evaluated and subjects should be asked for signs and symptoms suggestive of an immune-related event. Subjects who develop an ECI thought to be immune-related should have additional testing to rule out other etiologic causes. If lab results or symptoms indicate a possible immune-related ECI, then additional testing should be performed to rule out other etiologic causes. If no other cause is found, then it is assumed to be immune-related.

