3.2 Secondary Objective(s) & Hypothesis(es)

1. To determine changes in PD-L1 expression following irradiation
 - a. Hypothesis- irradiation will increase inflammation and PD-L1 expression
2. To determine the overall response rate as a function of PD-L1 expression
 - a. Hypothesis- higher rates of PD-L1 expression will be associated with higher overall response rates
3. To evaluate median progression free survival and overall survival
 - a. Hypothesis- based on limited data from previous studies the expected rate of DFS and OS are approximately 30% and 50% respectively
4. To determine the rate of immune related adverse events in patients receiving immunotherapy following radiation with or without systemic therapy
 - a. Hypothesis- The rate of immune related events post radiation will be similar to that of the baseline rate receiving immunotherapy in the metastatic setting
5. To determine the rate of distant metastases
 - a. Hypothesis- based on limited data from previous studies the expected rate of distant metastases is approximately 33%

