5.2.1.2 Dose Modification

Adverse events (both non-serious and serious) associated with pembrolizumab exposure may represent an immunologic etiology. These adverse events may occur shortly after the first dose or several months after the last dose of treatment. Pembrolizumab must be withheld for drug-related toxicities and severe or life-threatening AEs as per Table 3 below. See Section 5.6.1 for supportive care guidelines, including use of corticosteroids.

Table 3

Dose Modification Guidelines for Drug-Related Adverse Events

Toxicity	Hold Treatment For Grade	Timing for Restarting Treatment	Discontinue Subject
Diarrhea/Colitis	2-3	Toxicity resolves to Grade 0-1.	Toxicity does not resolve within 12 weeks of last dose or inability to reduce corticosteroid to 10 mg or less of prednisone or equivalent per day within 12 weeks.
	4	Permanently discontinue	Permanently discontinue
AST, ALT, or Increased Bilirubin	2	Toxicity resolves to Grade 0-1	Toxicity does not resolve within 12 weeks of last dose.
	3-4	Permanently discontinue (see exception below) ¹	Permanently discontinue
Type 1 diabetes mellitus (if new onset) or Hyperglycemia	T1DM or 3-4	Hold pembrolizumab for new onset Type 1 diabetes mellitus or Grade 3-4 hyperglycemia associated with evidence of beta cell failure.	Resume pembrolizumab when patients are clinically and metabolically stable.
Hypophysitis	2-3	Toxicity resolves to Grade 0-1	Toxicity does not resolve within 12 weeks of last dose or inability to reduce corticosteroid to 10 mg or less of prednisone or equivalent per day within 12 weeks.
	4	Permanently discontinue	Permanently discontinue
Hyperthyroidism	3	Toxicity resolves to Grade 0-1	Toxicity does not resolve within 12 weeks of last dose or inability to reduce corticosteroid to 10 mg or less of prednisone or equivalent per day within 12 weeks.
	4	Permanently discontinue	Permanently discontinue
Hypothyroidism	2-4	Therapy with pembrolizumab can be continued while treatment for the thyroid disorder is instituted	Therapy with pembrolizumab can be continued while treatment for the thyroid disorder is instituted.
Infusion Reaction	3-4	Permanently discontinue	Permanently discontinue
Pneumonitis	2	Toxicity resolves to Grade 0-1	Toxicity does not resolve within 12 weeks of last dose or inability to reduce corticosteroid to 10 mg or less of prednisone or equivalent per day within 12 weeks.

Toxicity	Hold Treatment For Grade	Timing for Restarting Treatment	Discontinue Subject

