5.6 Rescue Medications & Supportive Care

5.6.1 Supportive Care Guidelines

Subjects should receive appropriate supportive care measures as deemed necessary by the treating investigator. Suggested supportive care measures for the management of adverse events with potential immunologic etiology are outlined below. Where appropriate, these

measures may include the use of oral or intravenous treatment with corticosteroids as well as additional anti-inflammatory agents if symptoms do not improve with administration of corticosteroids. Note that several courses of steroid tapering may be necessary as symptoms may worsen when the steroid dose is decreased. For each disorder, attempts should be made to rule out other causes such as metastatic disease or bacterial or viral infection, which might require additional supportive care. The treatment guidelines are intended to be applied when the investigator determines the events to be related to pembrolizumab.

Note: if after the evaluation the event is determined not to be related, the investigator is instructed to follow the ECI reporting guidance detailed in Section 6.3.3.2, but does not need to follow the treatment guidance. Refer to Section 5.2.1 for dose modification.

It may be necessary to perform conditional procedures such as bronchoscopy, endoscopy, or skin photography as part of evaluation of the event.

- **Pneumonitis:**

- For **Grade 2 events**, treat with systemic corticosteroids. When symptoms improve to Grade 1 or less, steroid taper should be started and continued over no less than 4 weeks.
- For **Grade 3-4 events**, immediately treat with intravenous steroids. Administer additional anti-inflammatory measures, as needed.
- Add prophylactic antibiotics for opportunistic infections in the case of prolonged steroid administration.

- **Diarrhea/Colitis:**

Subjects should be carefully monitored for signs and symptoms of enterocolitis (such as diarrhea, abdominal pain, blood or mucus in stool, with or without fever) and of bowel perforation (such as peritoneal signs and ileus).

- All subjects who experience diarrhea/colitis should be advised to drink liberal quantities of clear fluids. If sufficient oral fluid intake is not feasible, fluid and electrolytes should be substituted via IV infusion. For Grade 2 or higher diarrhea, consider GI consultation and endoscopy to confirm or rule out colitis.
- For **Grade 2 diarrhea/colitis** that persists greater than 3 days, administer oral corticosteroids.

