1. In the case that a patient initiates a subsequent anti-cancer therapy the 30 day follow up should occur prior to the first dose of the new therapy and patients will move to survival follow up.
2. Vital signs should include temperature, pulse, respiratory rate, weight and blood pressure. Height will be measured at screening only.
3. Vital signs will be taken prior to the administration of each dose of trial treatment and at discontinuation of each treatment.
4. ECOG status will be evaluated prior to the administration of each dose of trial treatment and at discontinuation of each treatment.
5. Screening lab will be assessed within 14 days of first treatment.
6. After cycle 1, pre-treatment labs can be drawn up to 72 hours pre-dose.
7. The baseline CT scan can be from before study enrollment as long as the scan is within 4 weeks of study treatment.
8. Archival tissue from a biopsy prior to radiation treatment with or without systemic therapy should be requested.
9. All patients will have a biopsy prior to the start of study treatment. This specimen may be obtained up to 6 weeks (42 days) prior to initiation of treatment on Day 1 and following completion of RT/CRT. This pre-treatment biopsy can be used to confirm residual disease.
10. Patients will have a research biopsy after completion of the 4th treatment cycle or at study discontinuation if they come off treatment before cycle 4. There will be no additional biopsy for patients who stay on treatment past 4 cycles.
11. Imaging during study treatment cycles will occur at the end of cycle 2 when clinically indicated and cycle 4 or at disease progression whichever comes first (required). Less frequent imaging is acceptable during the continuation cycles, although a minimum of every 8 weeks is recommended.
12. If a patient comes off trial for reasons other than disease progression imaging should be done every 9 weeks ±7 days
13. Information on SAEs will be collected for 90 days after the end of treatment. Any unexpected SAE that occurs more than 90 days after drug administration but is possibly, probably or definitely attributed to drug administration will be recorded and reported.
14. Patients will have a repeat ENT evaluation for resectability status after completion of the 4th treatment cycle or at study discontinuation if they come off treatment before cycle 4. There will be no additional ENT evaluation for patients who stay on treatment past 4 cycles

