6.2.2.7 Adverse Event (AE) Monitoring

The investigator or qualified designee will assess each subject to evaluate for potential new or worsening AEs as specified in the Trial Flow Chart and more frequently if clinically indicated. Adverse experiences will be graded and recorded throughout the study and during the follow-up period according to NCI CTCAE Version 4.0 (see Section 10.2). Toxicities will be characterized in terms regarding seriousness, causality, toxicity grading, and action taken with regard to trial treatment.

For subjects receiving treatment with pembrolizumab all AEs of unknown etiology associated with pembrolizumab exposure should be evaluated to determine if it is possibly an event of clinical interest (ECI) of a potentially immunologic etiology (termed immune-related adverse events, or irAEs).

Please refer to section 6.3 for detailed information regarding the assessment and recording of AEs.

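### Collection of non-serious immune-related adverse events starting more than about 30 days after the last dose is not assured, so the irAE rate for secondary objective 4 may be understated

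*Combined protocol and SAP*

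**What the plan says.** **Objective.** Section 3.2, objective 4: "To determine the rate of immune related adverse events in patients receiving immunotherapy following radiation with or without systemic therapy". Its hypothesis: "The rate of immune related events post radiation will be similar to that of the baseline rate receiving immunotherapy in the metastatic setting". No baseline figure is given, and section 7.1 contains no irAE definition, ascertainment window or analysis.

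**Timing of immune events.** Section 5.2.1.2: "These adverse events may occur shortly after the first dose or several months after the last dose of treatment".

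**Ordinary adverse events.** Section 6.3: "All adverse events will be recorded from the time the consent form is signed through 30 days following cessation of treatment"; the same sentence then adds recording at each examination. Section 5.8 also uses 30 days, unless otherwise specified. Section 6.2.5.3.1 records all events before a safety visit held about 30 days after the last dose.

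**Later contacts.** In the flow chart (6.1), adverse event review at follow-up and survival contacts carries footnote 13: "Information on SAEs will be collected for 90 days after the end of treatment". The rest of the footnote concerns unexpected, attributable serious events after day 90.

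**Events of clinical interest (ECIs).** Section 6.3.3.2 sets a 90-day window for "ECIs (both non-serious and serious adverse events) identified above from the date of first dose through 90 days following cessation of treatment", cut short at 30 days after new anticancer therapy. Two items are listed: overdose without symptoms or laboratory abnormality, and raised AST or ALT with raised bilirubin and no marked rise in alkaline phosphatase.

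**Immune events treated as ECIs elsewhere.** Section 6.2.2.7 asks whether an event is "possibly an event of clinical interest (ECI) of a potentially immunologic etiology (termed immune-related adverse events, or irAEs". Section 5.5.2 permits steroids for ECIs of suspected immune cause. Section 5.6.1, for events judged unrelated after evaluation, says "the investigator is instructed to follow the ECI reporting guidance detailed in Section 6.3.3.2". The last paragraph of 6.3.3.2 itself discusses immune-related ECIs.

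**The concern.** Several sections assume that immune events are ECIs and so have the 90-day window. The list that defines that window leaves most of them out. On the narrow reading, a non-serious pneumonitis, colitis, thyroid or skin event starting six weeks after the last dose is neither a serious event nor a listed ECI, and it falls outside the 30-day window. On the broad reading it is recorded at the next follow-up examination. Two sites could follow the protocol in good faith and collect different data.

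This affects objective 4 in particular because patients who go to surgery stop after four cycles, so much of the period in which late immune events could appear falls after treatment. Any events lost would lower the cumulative rate. The primary response endpoint is not affected.

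**Working it through.** The plan states no figure for the irAE rate, its precision or the share of late events, so there is nothing to reproduce. The check is a reading of the windows plus simple arithmetic.

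**1. Which window applies to an event starting more than 30 days after the last dose?**

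| Event | Provision | Collected to day 90? |
|---|---|---|
| Serious | 6.3.3.1; footnote 13 | Yes, unless new anticancer therapy starts earlier |
| Hepatic laboratory criterion, serious or not | 6.3.3.2, item 2 | Yes, subject to its own cut-off |
| Other non-serious irAE | 5.8, 6.2.5.3.1, footnote 13 | Not provided for |
| Other non-serious irAE | 6.2.2.7 (recording in the follow-up period); 6.3 (each examination) | Supported, with no end date |

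The last two rows conflict.

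**2. Calendar for a patient who stops after cycle 4** (21-day cycles, no delays, cessation taken as the last dose):

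- Dose 4: 1 + 3 × 21 = day 64.
- 30-day window ends: 64 + 30 = day 94.
- 90-day window ends: 64 + 90 = day 154.
- Uncertain period: days 95 to 154, which is 60 of 90 days (67%).

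The 67% is a share of time, not of events. The edges move with the ±7-day visit window and with new therapy.

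**3. Are contacts available in that period?** Counting from the last dose, 8-weekly visits fall on days 64 + 56 = 120 and 64 + 112 = 176. The first lies inside the gap, and the second can ask back to day 154. For patients in survival follow-up, a 12-weekly call would fall on about day 64 + 84 = 148.

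**4. Size.** One patient whose only irAE is missed changes the rate by 1/24 = 4.2 points. As an illustration, let R be the true cumulative rate and f the share of irAE patients whose only irAE is non-serious, late and unrecorded. Then the observed rate is R × (1 − f). Both inputs are assumptions:

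| R | f | Observed | Fall (points) | Patients of 24 |
|---|---|---|---|---|
| 15% | 5% | 14.25% | 0.75 | 0.18 |
| 25% | 20% | 20% | 5.0 | 1.2 |
| 35% | 30% | 24.5% | 10.5 | 2.52 |

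If f = 0, or if sites do record these events at follow-up, the fall is zero. For scale, 6/24 (25%) has an exact 95% confidence interval of 9.8% to 46.7%.

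**The case against.** The strongest reply is that the protocol does not exclude late non-serious events. Section 6.2.2.7 has adverse events graded and recorded in follow-up, section 6.3 adds each examination, and section 5.8 allows for exceptions. Footnote 13 does not say that only serious events are collected, and the ECI list is introduced by a word that can be read as non-exhaustive. A reader might infer that these events are never collected; the documents do not support that, and this part of the reply stands.

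It does not settle the matter. Section 6.2.2.7 takes its schedule from the flow chart and its detail from section 6.3. Section 6.2.5.3.2 lists the content of follow-up visits without adverse event review. The only extension section 5.8 goes on to state is for serious events. Section 5.5.1 records medications beyond 30 days only for serious events and ECIs. Whatever the introductory word means, the 90-day window is tied to the ECIs already listed.

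A reader might also infer a downward bias that favours the hypothesis of similar toxicity. That is not established. If the metastatic rate was collected over a similar 30-day window, the shorter window is the like-for-like one and a 90-day rate could look too high beside it. Understatement can be claimed only against the trial's own full cumulative rate.

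Finally, late serious events are covered, including important medical events that did not need admission, so what is at risk is mainly lower-grade events in a descriptive objective with a wide interval. That is fair and limits the weight of the point.

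**Conclusion.** The point holds as a conflict between collection windows. Non-serious irAEs starting more than about 30 days after the last dose, other than the hepatic criterion, have no assured collection, although the protocol expects late onset. The 30-day window and footnote 13 create the gap, and the ECI list fails to close it.

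The cumulative irAE rate may therefore be understated, by 4.2 points for each patient whose only irAE is missed. This is conditional on such events occurring and on sites following the narrow reading. The total cannot be estimated from the documents, and the direction against the metastatic rate is unknown. The point is worth correcting because the repair is cheap and decides what data objective 4 rests on; it does not threaten the trial's main conclusion.

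**What to change.** 1. In sections 5.8 and 6.3 and in footnote 13, state that adverse events of suspected immunologic cause, serious or not, are collected through 90 days after the last dose at contacts already scheduled: the 30-day visit, the 8-weekly visits, or the 12-weekly telephone contact after progression or new therapy. State the rule for new anticancer therapy, including whether the planned resection counts as such. Align sections 6.2.2.7 and 6.2.5.3.1 with this.
2. Reconcile the ECI list in 6.3.3.2 with sections 5.5.2, 5.6.1 and 6.2.2.7. Do not do this by making every suspected immune event an ECI: that would bring each low-grade event under 24-hour reporting and two-working-day forwarding to Merck from the first dose.
3. In section 7.1, define an irAE and report the rate through 90 days after the last dose, with the 30-day rate alongside for comparison with the metastatic setting.

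The cost is amendment wording, a few more adverse event entries and a possibly higher reported rate. Telephone ascertainment of mild events will be less complete than a visit. No new visit or procedure is needed.

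As a separate editorial matter, the flow chart marks blood count and chemistry at discontinuation while the discontinuation list in section 6.2.5.2 omits them; the two should be reconciled. Extra laboratory draws are not part of this fix.
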